 - ii. In addition to surveys, the clinic staff will be trained to observe which patients talk with whom, as well as, the frequency and approximate duration of the conversation. The staff will be instructed to continue to assign seating based on clinical necessity and patient preference. Research staff, while they are performing the surveys or the COACH intervention, will also make and record observed patient interactions. Furthermore seating assignments

will also be collected. This data will be coded, patients will be de-identified for the analysis.

- iii. COACH is a behavioral communication intervention designed specifically for ESRD patients pursuing kidney transplantation. The COACH program (appendix) consists of four modules: 1) Kidney transplant options, 2) Discussing your transplant options, 3) Requesting living donation, and 4) Maintaining positive relationships. The content and teaching strategies were guided by the concepts of social cognitive theory as well as principles of adult learning and communication skills²²⁻²⁵. Another study coordinator will conduct the intervention in four, face to face, one hour sessions in the HD clinic. Patients will receive the accompanying handbook and video for the COACH intervention.
- iv. Using the data collected from the original survey and social network analysis, we will randomly select one transplant eligible patient (based on network attribute (most-clustered or most-central) per shift to participate in the COACH intervention.

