AIM3: Compare and contrast the diffusion of knowledge, attitudes, and behaviors regarding transplantation through HD social networks by targeting either the most central or the most clustered members of the network to disseminate a transplant education intervention. **H3:** Targeting patients with high clustering coefficients will be the most effective method for the spread of knowledge and favorable attitudes toward transplantation, and completing steps toward transplantation as compared to targeting by centrality.

Rationale: Previous studies have shown that barriers to transplantation tend to be less about information but rather behaviors related to completing the transplant steps^{1,2,4,13}, thus dense social networks are likely to be more effective in changing behavior and participating in a social network than diffuse networks, which are more effective at spreading novel information³²⁻³⁴.

Patient Recruitment, Eligibility, and Retention AIM 3: One year after the initial survey, we will use a targeted network intervention to measure the spread of information, attitudes, and behaviors. We will target transplant eligible patients based on their clustering coefficient or their betweenness centrality to participate in the COACH education using data collected in AIMS 1 and 2.

Recruitment Goals: Based on previous research^{1,4}, we anticipate approximately half the patients would be eligible for a kidney transplant but not on the list. If 250 patients participate in **AIM 1 and 2**, then at least 125, or approximately 10 patients per shift will be eligible for the intervention. The intervention will target either the two most central transplant eligible patients or the two most clustered patients to participate in the COACH education. As this is a social network intervention, although we are targeting only two patients per shift, all the patients on that shift are considered exposed to the COACH education. To prevent selecting a patient that is both relatively central and clustered, the patients selected by centrality will have a centrality greater than 1 standard deviation (SD) from the mean and a clustering less than 1 SD from the mean. Conversely, the

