Staggered Surveys: We propose a pre-post design to assess the impact of the COACH education on patients' transplant-related knowledge and behaviors. Before administering the COACH education, we will survey targeted patients to assess changes in knowledge and behaviors towards transplant from the baseline survey. As another measure of the impact of the COACH intervention, patients not receiving the intervention will serve as controls and will be surveyed along with those receiving the intervention; we will then assess within and between group differences in transplant-related knowledge and behaviors. To assess the dissemination of information contained in the COACH intervention, all patients will be surveyed at 3-months post-intervention. The follow-up surveys will determine the sources of these changes (eg. self-reading after the survey, the COACH intervention, or discussing with other patients). Finally, during Year 4, one year post-intervention, a final survey will be administered to the all the patients in both clinics to assess retention of information and change in attitudes and behaviors of those who participated in COACH and the spread of information and behaviors to the patients who were not targeted.

Clinical Data: In addition to the survey data, we will collect patient transplant listing status, living donor evaluations from participants' respective transplant centers.

Analytic plan AIM3: To test **H3** we will assess the successful spread of the intervention by evaluating the difference in the primary outcome of completion of steps toward transplantation between patients being exposed via the most clustered (Cluster) members versus the most central (Central). We will use repeated surveys to measure our secondary outcomes include change in knowledge, attitudes, behaviors of the patients either directly exposed to the intervention or those who were exposed indirectly through the social network.

Primary Outcomes: 1) Differences in patient knowledge, 2) Differences in transplant steps completed

Secondary Outcomes: 1) Completion of transplant work-up, 2) Asking for a living donor

Independent Variables: Intervention assignment to Cluster or Central

Covariates: Age, Marital Status, insurance, transplant eligibility, HD shift, HD Clinic, network attributes

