Exposure: While only two patients per shift will receive the COACH intervention, all patients regardless of participation in the COACH education will be analyzed as exposed to the intervention via social spread. This will result in two groups for the primary analysis Cluster (MWF1 Cluster + TTS2 Cluster) and Central (MWF2 Central + TTS1 Central)

Analysis: To measure global changes, we will use a t-test to test changes in knowledge and changes in completion of steps between Cluster and Central. Individual level transfer of information will be analyzed with a

Markov chain Monte Carlo accept-reject procedure in the chain⁵⁸. We will examine the correlation in changes of a patient's(ego) knowledge with his or her first degree alter and measure the decay in correlation as the degree of the alter increases. We will also examine the ego's distance (how many links the patients are from each other) from the alter receiving the intervention. In addition, we will use Gaussian Conditional Random Fields (GCRF) methods to model a patient's stage in the transplant process by taking into account various factors such as personal demographics, social influence of alters, and global trends of HD shift and clinic⁵⁹. We will examine the characteristics of the patients disseminate and receive information. The data directly measuring the spread of information, influence, and behavior within the network from this experiment will be used to validate and strengthen the social network model developed in AIM1 and AIM2.

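### Untrained patients are called controls for COACH although the SAP counts them as exposed, and Aim 2 follow-up runs into the COACH period without a cut-off; the primary Cluster-Central test is not affected

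*SAP*

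**What the plan says.** **The comparator.** SAP AIM3, Staggered Surveys, and Protocol 7.d.v describe a pre-post design. They then add a second measure of COACH impact, in which "patients not receiving the intervention will serve as controls and will be surveyed along with those receiving the intervention", with differences assessed within and between groups.

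**Exposure.** SAP AIM3, Recruitment Goals, states that "all the patients on that shift are considered exposed to the COACH education". The Exposure paragraph repeats that "all patients regardless of participation in the COACH education will be analyzed as exposed to the intervention via social spread". The Analytic plan for AIM3 speaks of patients "either directly exposed to the intervention or those who were exposed indirectly through the social network". Table 3 assigns every shift in both clinics to Cluster or Central.

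**Recipients.** The SAP says "While only two patients per shift will receive the COACH intervention". Protocol 7.d.iv says "we will randomly select one transplant eligible patient" per shift. Recipients must be transplant eligible and are picked on network position. Central recipients need high centrality and "a clustering less than 1 SD from the mean"; Cluster recipients need the reverse. The AIM3 list reads "Covariates: Age, Marital Status, insurance, transplant eligibility, HD shift, HD Clinic, network attributes", but the only independent variable named is assignment to Cluster or Central.

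**Aim 2.** The Limitations paragraph calls Aims 1 and 2 observational. The covariates contain no term for COACH, arm or shift. The temporal network model relates a patient's current transplant step to the baseline and current steps of linked patients. Under AIM 1, Analysis, links are revised at each survey wave. The Timeline marks Aim 2 follow-up from Year 2 Q1 to Year 3 Q4 and the Aim 3 experiment from Year 3 Q1 to Year 4 Q1.

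**The concern.** A control group for COACH has to show what happens without COACH. Here every untrained patient shares a shift with a recipient, and the trial's hypothesis is that content spreads along links. If it does, untrained patients improve too and the difference narrows, so a COACH that works and spreads could be read as weak. Protocol section 4 adds to the ambiguity: it uses a comparison of targeted patients with others on their shift to measure spread. A small difference would then mean good spread under one section and low impact under the other.

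Recipients also differ from the rest in eligibility and network position, which can move the contrast either way. The covariates that might help are listed for Aim 3 but not tied to this contrast.

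For Aim 2, H2 asks whether patients in dense networks resemble each other in attitudes and steps. COACH content passing along links could create such likeness. Receipt of COACH is itself allocated by clustering or centrality, and clustering is a main predictor in H2. Data collected after COACH starts could therefore carry the trial's own intervention into a result reported as observational.

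**Working it through.** **1. The plan's own figures.** SAP, Sample size and power AIM3, uses a two-sided t-test at alpha 0.05. Recomputed power is 80.0% for effect size 1.06 with 15 per arm, 82.1% for one step (1.06/2 = 0.53) with 60 per arm, and 80.4% for half of 1.2 (0.6) with 45 per arm. All three stated figures reproduce. All concern Cluster against Central, which is defined by shift and includes everyone, so they do not use the trained-untrained split.

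**2. Group sizes.** Two clinics with 6 shifts each give 12 shifts. Two recipients per shift gives 24 trained and, of the SAP's 120 patients, 96 untrained. One per shift gives 12 and 108.

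**3. Size of the contrast (illustration).** Let *s* be the share of the direct effect that reaches an untrained patient. The documents give no value, so *s* is assumed. Read the SAP's knowledge effect of 1.2 as a direct effect in SD units, which is also an assumption.

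- If all untrained patients receive *s*, the contrast is 1.2(1 − *s*).
- If only linked patients receive *s*, it is 1.2(1 − *qs*), where *q* is the linked share among the untrained. The pilot had 31/46 = 0.674 of patients linked. Taking all recipients as linked, *q* = (0.674 × 120 − 24)/96 = 0.592 for 24 recipients, and (0.674 × 120 − 12)/108 = 0.638 for 12.

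Power, two-sided t-test, alpha 0.05, patients treated as independent, no adjustment:

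| *s* | 24 v 96, all | 24 v 96, linked only | 12 v 108, all | 12 v 108, linked only |
|---|---|---|---|---|
| 0 | >99% | >99% | 97% | 97% |
| 0.25 | 97% | 99% | 84% | 91% |
| 0.50 | 74% | 96% | 50% | 76% |
| 0.75 | 26% | 83% | 17% | 53% |

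At *s* = 0.50 with 24 recipients, for example, the contrast is 1.2 × 0.50 = 0.60 SD if all receive it, and 1.2 × (1 − 0.592 × 0.50) = 0.845 SD if only linked patients do. In the pilot, linked means linked to anyone, not to a recipient, so the loss could be smaller still.

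**4. Aim 2 overlap.** Number the quarters from Year 1 Q1. Aim 2 follow-up covers 5 to 12 and Aim 3 covers 9 to 13. They share 9 to 12, which is 4 of 8 Aim 2 quarters. Waves 1, 2, 3 and 4 fall in Year 2 Q1, Year 3 Q1, Year 3 Q2 and Year 4 Q1. Wave 2 is taken as the survey held before COACH, and Wave 4 lies outside the Aim 2 row. So one of the three survey waves in the Aim 2 window, Wave 3, comes after COACH. Attitudes come from surveys and links are updated by wave, so their overlap is limited to Wave 3. Transplant steps taken from records accrue through all four shared quarters.

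**The case against.** The strongest reply is that this is mostly a wording slip in a supplementary measure within a pilot. The SAP itself already describes untrained patients as indirectly exposed. The pre-post design reports within-group change, which would show improvement among untrained patients. Follow-up surveys ask where new knowledge came from, including talk with other patients. The AIM3 Analysis examines distance from the recipient and the decay of correlation with distance. These safeguards stand, and they make it less likely that a spreading COACH would be read as weak. They do not redefine the between-group contrast, which is still presented as a measure of COACH impact against controls.

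On Aim 2, recipients are selected with data from Aims 1 and 2, and the AIM3 Analysis would use experiment data to validate a model developed in those aims. That implies an order. Protocol 7.c's yearly analysis is likewise compatible with analysing H2 before COACH. The Aim 2 Limitations also disclaim separating like-minded grouping from spread. All this is fair, but no cut-off is stated, and nothing says the validation data are kept out of the Aim 2 fit.

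A reader might infer from four quarters in eight that half of the Aim 2 data are contaminated. The documents do not support that: it is calendar overlap, and only one survey wave in the window follows COACH.

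**Conclusion.** The point holds and is minor. The SAP and Protocol call patients controls whom the SAP elsewhere counts as exposed, and no COACH-free shift exists. What the contrast can estimate is direct minus indirect exposure, among patients also selected on eligibility and network position. The Aim 2 plan leaves room for COACH to enter H2, with unknown direction and size.

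Three stronger readings should be resisted.

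- **That the primary analysis lacks a valid comparator.** It compares two targeting strategies by shift and needs no unexposed group. Neither fault changes its groups, sample size or power. This says nothing about other features of that test.
- **That power for the trained-untrained contrast is as low as 17% or 26%.** Those figures need 75% spill-over to every untrained patient. With two recipients per shift and spill-over only to linked patients, power stays above 80% across the range shown. All the figures depend on an assumed *s*, on reading 1.2 as a direct effect in SD units, and on independent patients. The SAP claims no power here.
- **That H2 support would be an artefact of COACH.** The documents show a possible route, not a bias of known sign or size.

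**What to change.** 1. In SAP Staggered Surveys and Protocol 7.d.v, replace the term controls with patients exposed indirectly. Report the contrast among transplant-eligible patients, adjusted for the covariates already listed for Aim 3, with network attributes as measured before COACH. Present it as a descriptive direct-minus-indirect difference beside the within-group changes, and do not interpret it as the effect of COACH. Reconcile one recipient per shift (Protocol 7.d.iv) with two (SAP Recruitment Goals and Exposure).
2. In the Analytic Plan for AIM 2, base the H2 analysis on data collected before COACH starts: Waves 1 and 2, and steps to that date. Label any H2 analysis that uses later data as post-intervention. Include in it the distance-from-recipient measure already planned under AIM3, with COACH receipt and shift. Receipt and shift alone would not capture spread along links.
3. In the AIM3 Analysis, state that validation of the Aim 2 model uses data not used to fit it.

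The cost is wording and a few model terms. No new data are needed, since patients are already surveyed at all four waves. There are two downsides. The pre-COACH H2 estimate has one year of follow-up and is less precise. And because network rank decides who is trained, few untrained patients are comparable on network position, so the adjusted contrast stays descriptive.

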Limitations: If the targeted patient refuses to participate, we will select another two transplant eligible patients to participate in the intervention based on their clustering and centrality. The network attributes of the patients if they refuse to participate will be analyzed and can inform AIMS 1 and 2 as well as recruitment strategies for future studies. In the unlikely event no patients on the shift participate in the COACH education, they will be analyzed as intention to treat. Since we are measuring change in knowledge using repeated surveys we are at risk for a learning effect⁶⁰. For this reason on the repeated survey questionnaires, we will also assess where the new knowledge came from patient interactions or self-reading after the survey. Given the focus of the proposed research on urban and suburban locales, future research is indicated to see if this social network mapping and intervention can also be used in rural settings, especially since recent studies shown many patients in rural southeast are disadvantaged regarding transplantation⁶¹.

Sample size and power AIM3: Using the data from our previous HD clinic social network study, we expect the patients in the Clustering targeted intervention to complete at least 2 more steps in the transplant work-up than those in the Centrality intervention (7, SD 1.5 vs 5, SD 1.7, p=0.03). The observed effect size was 1.06 or a difference of 2 steps. We estimate at least 10 patients per shift will be exposed to the intervention either directly through participation in the intervention or indirectly through information/behavior spread through the social network. Both clinics have 6 shifts, and we would have 60 patients assigned to each intervention condition. Based on a two tailed t-test, a total sample of 30 (15 in each treatment arm) would yield 80% power at significance level $\alpha = 0.05$ to detect a difference of 2 steps. With 120 patients (60 patients in each treatment arm) we will be powered to detect a difference of 1 step. The COACH intervention produced a change in knowledge³ with an effect size of 1.2, thus if we expose 90 patients (45 in each arm) to the intervention, we will have the power to detect at least half that effect.

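### SAP Aim 3 contradicts itself on its primary outcome: steps alone in the narrative, knowledge and steps in the list below it, and nothing reconciles the two

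*SAP*

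**What the plan says.** The SAP's Analytic plan AIM3 assigns outcome roles twice.

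- **Narrative.** H3 is to be tested by comparing Cluster with Central on "the primary outcome of completion of steps toward transplantation", in the singular. The next sentence says that "our secondary outcomes include change in knowledge, attitudes, behaviors".
- **List directly below.** "Primary Outcomes: 1) Differences in patient knowledge, 2) Differences in transplant steps completed". The secondary outcomes listed after it are work-up completion and asking for a living donor. Attitudes are in neither list.

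Other sections that bear on the choice:

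- **H3 (SAP, AIM3)** says targeting by clustering will be most effective "for the spread of knowledge and favorable attitudes toward transplantation, and completing steps toward transplantation". It covers three domains joined by a conjunction.
- **Analysis (SAP, AIM3):** "we will use a t-test to test changes in knowledge and changes in completion of steps between Cluster and Central". It gives no order and no adjustment.
- **Sample size and power AIM3** treats each outcome separately. Cluster patients are expected to "complete at least 2 more steps in the transplant work-up than those in the Centrality intervention", at two-tailed alpha 0.05. For knowledge, with 45 patients per arm, "we will have the power to detect at least half that effect", meaning half of 1.2.
- **Protocol section 7.d.vi** sets a general threshold of p below 0.05. The protocol names no primary outcome for the intervention.

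**The concern.** Knowledge cannot be both secondary and the first-listed primary outcome. The conflict matters when the two t-tests disagree, because the conclusion then turns on which reading is applied, and that could be settled after the results are known.

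| Significant in favour of Cluster | Steps alone decides | Either suffices | Both required |
|---|---|---|---|
| Steps only | H3 supported | H3 supported | not supported |
| Knowledge only | not supported | H3 supported | not supported |
| Both | H3 supported | H3 supported | H3 supported |

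The SAP's own rationale makes disagreement believable. It describes dense networks this way: "more effective in changing behavior and participating in a social network than diffuse networks, which are more effective at spreading novel information". On that argument, Cluster targeting could win on steps and not on knowledge.

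**Working it through.** **1. Reproduce the SAP's sizing** (two-sample t-test, two-sided 0.05, patients independent).

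- Steps, d = 1.06, 15 per arm: power 80.0%. This matches the SAP.
- Steps, 1 step, 60 per arm: d = 1.06/2 = 0.53 gives 82%. With the stated SDs, the pooled SD is √[(1.5² + 1.7²)/2] = 1.60, so d = 0.62 and power is 92%. Either agrees with the SAP's claim.
- Knowledge, d = 1.2/2 = 0.6, 45 per arm: power 80.4%. This matches if the full 0.05 is used.

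Each sizing spends the whole 0.05. That fits steps alone, or both required with each tested at 0.05. It does not fit an either-suffices rule that controls error.

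**2. Type I error under each reading**, assuming each test holds its own 5% level. The documents give no correlation between the outcomes, so 0 and 0.5 are assumed.

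- Steps alone: 5% two-sided, 2.5% in the direction of H3.
- Both required: with no true difference on either outcome, it cannot exceed the single-test level.
- Either suffices, correlation 0: 1 − 0.95² = 9.75% two-sided; 1 − 0.975² = 4.9% in the direction of H3.
- Either suffices, correlation 0.5: 1 − P(|Z₁| < 1.96 and |Z₂| < 1.96) = 9.1% two-sided; 1 − P(Z₁ < 1.96 and Z₂ < 1.96) = 4.5% in the direction of H3.

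**3. How often exactly one test is significant.** Steps d = 1.06 is the SAP's expectation. A knowledge effect of 0.6 between arms is an assumption: the 1.2 behind it is the change COACH itself produced, not a Cluster-versus-Central difference.

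- *Independent patients.* Steps power at 60 per arm is 99.99%, so the split rate is close to one minus knowledge power: 1 − 0.804 = 19.6% at 45 per arm, and 1 − 0.903 = 9.7% at 60 per arm. Simulation at correlations 0, 0.5 and 0.7 agrees, at about 10% to 20%.
- *Shift-level test.* There are 12 shifts, 6 per arm, taken as 10 patients each. The variance of a shift mean in SD² units is ICC + (1 − ICC)/10, which is 0.118, 0.145 and 0.190 at assumed ICC 0.02, 0.05 and 0.10. A t-test on shift means (10 df, correlation 0.5) gives a split in 22%, 30% and 40% of trials.
- *Knowledge d = 1.2.* Splits almost never occur with independent patients, and occur in at most about 4% of trials in the shift-level test.

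**The case against.** The strongest reply is that the narrative sentence is itself a rule: it ties the test of H3 to steps. That is correct, and a reader who infers that the SAP has no decision rule at all goes too far. The SAP states a steps-only rule and then contradicts it under an explicit heading for primary outcomes. H3's wording and the separate power statements leave the conflict open.

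A reader might also infer that the plan carries a 9.75% error rate. It does not. That figure needs an either-suffices rule, which no section states. The narrative points to steps alone and H3's conjunction points to requiring both, and neither inflates error.

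Nor should a reader conclude that a split is nearly certain. If steps differ by d = 1.06 and knowledge does not differ at all, steps alone is significant in about 95% of trials. That is little more than 1 − 0.05, fixed by the assumption. The SAP's rationale could equally mean that knowledge favours Central, which is not modelled here.

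Two further points stand. The SAP calls the study a pilot and specifies both tests in advance, so strict family-wise control carries less weight. But it also states a directional hypothesis with a formal power calculation, so a verdict on H3 will be expected. And the sponsor could legitimately keep both outcomes primary, since H3 and the list each name knowledge first.

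**Conclusion.** The contradiction is real and sits within one section of the SAP. Its consequence is conditional: it changes the verdict on H3 only when the two tests disagree. That happens in about 10% to 20% of trials with independent patients, and about 22% to 40% in a shift-level test. Both ranges rest on the assumed between-arm knowledge effect of 0.6, and the second also on the assumed ICCs. The stated sample sizes are not wrong on this account. The conflict should be resolved before outcome data are analysed.

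**What to change.** Name change in transplant steps completed as the single primary outcome of Aim 3; it is the only outcome called primary in both places. Move knowledge to the secondary list, add attitudes there, and delete the conflicting line. Alpha stays at 0.05 and the stated sizing for steps is unchanged. The cost is SAP wording, with no extra patients or data, and knowledge loses primary status.

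If the sponsor prefers two primary outcomes, state the success rule (both required at 0.05, or Holm) and restate power under it. For scale, with independent patients, testing knowledge at 0.025 (the first Holm step) lowers its power at d = 0.6 from 80% to 71% at 45 per arm, and from 90% to 84% at 60 per arm. The restated power should allow for assignment by shift.

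The same edit can name the time point for the t-test. The Staggered Surveys paragraph has surveys at 3 months and one year, and the Analysis paragraph names neither. That is a separate missing detail, not part of the contradiction.
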